7.3.2.3. Excluded analyses for efficacy

The following protocol defined analyses will not be performed anymore. These will be addressed in the ancillary MALARIA-095 study.

Incident infection:

Analysis performed at Month 33:

- Vaccine efficacy of R012-20 versus Control group over D0-M26 (all episodes, ES).
- Vaccine efficacy of R012-14 versus Control group over D0-M26 (all episodes, ES).
- Vaccine efficacy of Fx012-14 versus Control group over D0-M26 (all episodes, ES).
- Vaccine efficacy of Fx017-20 versus Control group over D0-M26 (all episodes, ES).
- Incremental efficacy of Fx017-20 versus R012-20 over M20-M32 (all episodes, PPS).
- Incremental efficacy of Fx012-14 versus R012-14-mD over M14-M26 (all episodes, ES).

Analysis performed at Month 50:

- Vaccine efficacy of R012-20 versus Control group over D0-M38 (all episodes, ES).
- Vaccine efficacy of R012-20 versus Control group over D0-M50 (all episodes, ES).
- Vaccine efficacy of R012-14 versus Control group over D0-M38 (all episodes, ES).
- Vaccine efficacy of R012-14 versus Control group over D0-M50 (all episodes, ES).
- Vaccine efficacy of Fx012-14 versus Control group over D0-M38 (all episodes, ES).
- Vaccine efficacy of Fx012-14 versus Control group over D0-M50 (all episodes, ES).
- Vaccine efficacy of Fx017-20 versus Control group over D0-M38 (all episodes, ES).
- Vaccine efficacy of Fx017-20 versus Control group over D0-M50 (all episodes, ES).
- Incremental efficacy of Fx012-14 versus R012-14-mD over M26-M38 (all episodes, PPS).
- Incremental efficacy of Fx012-14 versus R012-14-mD over M38-M50 (all episodes, PPS).

7.3.2.4. Additional considerations for efficacy analyses

Schoenfeld residual test will be used to test the independence between residuals and time. This test will be performed on the primary objective and on the secondary objective of incremental efficacy over the 12-month period post-dose 3 of a schedule with a fractional dose at month 7 versus 3 full doses

7.3.2.5. Additional considerations for analyses for cases averted

For each site and overall, the number of cases of clinical malaria will be calculated (difference between incidences of control group and vaccine groups, expressed per 1000 population vaccinated) for each 3-monthly time period and totaled over the follow-up periods month [0-14], [0-26], [0-32], [0-38] and [0-50].

7.3.2.6. Additional considerations for exploratory analyses

Malaria species

A listing of cases with *P. ovale* parasite, *P. malariae* malaria and *P. vivax* parasites by group will be provided.

Waning efficacy

Waning efficacy will be explored by plots of hazard ratios of study groups versus the control over time. Piece wise cox models will be performed comparing Fx017-20, Fx012-14, R012-20, R012-14 to the control over periods of 6 months to estimate hazard ratios. The Hazard ratios obtained from the models will be plotted in graphs.

7.4. Immunogenicity

7.4.1. Analysis of immunogenicity planned in the protocol

The primary analysis of immunogenicity will be based on the PPS for immunogenicity; however, analyses on the ES will also be performed.

In the immunogenicity subset (first 50 subjects enrolled in each group), the percentage of subjects with seropositive levels of anti-CS (proportion of subjects with anti-CS antibody concentrations greater than or equal to 1.9 EU/ml) with 95% CI will be determined at specified blood sampling timepoints in each group (see Section 2 – Sampling schedule). Anti-CS antibody concentrations will be summarized by geometric mean concentrations (GMCs) with 95% CI. Anti-CS antibody concentrations one month after the third dose and each subsequent dose of study vaccine will also be investigated using reverse cumulative distribution (RCD) curves.

The seroprotective level for anti-HBs is ≥ 10 mIU/ml. In the immunogenicity subset, the percentage of subjects with protective levels of anti-HBs (≥ 10 mIU/ml) with 95% CI will be determined at specified blood sampling timepoints in each group (see Section 2 – Sampling schedule). Anti-HBs antibody concentrations will be summarized by GMCs with 95% CI. Anti-HBs antibody concentrations one month after the third dose and each subsequent dose of study vaccine will also be investigated using RCD curves.

For the analysis of the tertiary objective, avidity/affinity index and avidity maturation will be summarized by mean, SD, median and quartile.

7.4.2. Additional considerations

Statistical methods for Geometric Mean Concentrations

GMCs and associated two-sided 95% CIs will be computed for each group at each available immunogenicity monitoring timepoint. The 95% CI for the mean of log-transformed concentration will be obtained assuming that log-transformed concentrations are normally distributed with unknown variance. Logarithmic transformations use base 10. The 95% CI for the GMC will then be obtained by exponential transformation (base 10) of the 95% CI for the mean of the log-transformed concentrations.

Reverse cumulative distribution curves

RCD curves for antibody concentrations will be plotted: the x-axis represents the antibody concentrations value (log-10 scale), while the y-axis represents the percentage of subjects having a log-transformed antibody value greater or equal to the corresponding x-value.

Statistical methods for seropositive/seroprotection rates

The percentage of subjects seropositive/seroprotected and associated two-sided 95% Clopper-Pearson CIs will be computed by vaccine group at each available immunogenicity monitoring.

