1.2. Rationale for the study

GSK Biologicals and PATH are committed to develop a malaria vaccine for reduction of malaria disease burden in children and contribution to the malaria elimination goal. Characterization of an optimal dosing regimen and boosting schedules will be critical.

The results of the efficacy study MALARIA-055 PRI, including the long term follow-up data and efficacy of the fourth dose administered 18 months after the third dose, and the preliminary results of MALARIA-071 were reviewed by the European Medicines Agency (EMA) during the assessment of the initial Application of the RTS,S/AS01_E candidate vaccine. The EMA asked the company to address the following points in ongoing or future studies: 1) the timing of the fourth dose and evaluation of the safety and efficacy of an early fourth dose; 2) the efficacy and safety of multiple yearly doses and whether the vaccine predisposes to some degree of hyporesponsiveness to sequential doses; and 3) the plans to further investigate the potential utility of a delayed and fractionated third dose schedule in the target age range.

The current study is designed to address these points in the pediatric population. It aims to:

- Establish proof-of-concept (POC) for a fractional (Fx) dose schedule under conditions of natural exposure.
- Establish the role of third dose spacing in a fractional dose schedule.
- Describe the effect of an earlier full fourth dose at Month 14.
- Describe the effect of multiple fractional or full yearly doses.

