11.2. Secondary endpoints

- **Efficacy:**
 - The occurrence of clinical malaria meeting the primary and secondary case definitions from Day 0 up to Month 50.
 - The occurrence of incident *P. falciparum* infections from Day 0 to Month 50.
 - The prevalence of *P. falciparum* infections defined by positive blood slide at each cross-sectional survey.
- **Immunogenicity: Immune response to the CS and HBs antigens (immunogenicity subset)**
 - *Anti-CS antibody concentrations and seropositivity measured before Dose 1, one month post-Dose 2 (group Fx017-mFxD only), before and one month post-Dose 3, before and one month after Dose 4, before and one month after each yearly dose and at study end (Month 50).*
 - Anti-HBs antibody concentrations and seropositivity measured before Dose 1, one month post-Dose 2 (group Fx017-mFxD only), before and one month post-Dose 3, before and one month after Dose 4, before and one month after each yearly dose and at study end (Month 50).

Amended 14 November 2019

- **Safety**
 - The occurrence of SAEs (all, fatal and related) during the whole study period according to the MedDRA classification.
 - The occurrence of AEs and SAEs leading to withdrawal from further vaccination from Dose 1 (Day 0) up to Month 50, according to the MedDRA classification.
 - The occurrence of severe malaria cases and cerebral malaria cases during the whole study period.
 - The occurrence of pIMDs from Day 0 up to Month 50, according to the MedDRA classification.
 - The occurrence of meningitis from Day 0 up to Month 50, according to the MedDRA classification.
 - The occurrence of seizures within 30 days (day of vaccination and 29 subsequent days) after each dose of study vaccine, according to the MedDRA classification.
 - The occurrence of generalized convulsive seizure within seven days (day of vaccination and six subsequent days) after each dose of study vaccine, according to the Brighton collaboration guidelines [[Bonhoeffer](#), 2004].

- The occurrence of unsolicited AEs within 30 days (day of vaccination and 29 subsequent days) after each dose of study vaccine, according to the MedDRA classification.
- The concentration of biochemistry (ALT, creatinine) and hematology (hemoglobin, WBC, platelets) parameters in the first 50 subjects (25 subjects per site) enrolled in each group (reactogenicity sub-cohort) before Dose 3, seven days post-Dose 3 and 30 days post-Dose 3.
- **Reactogenicity (reactogenicity sub-cohort)**

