3.2. Secondary objectives

Efficacy

- To assess the incremental vaccine efficacy against clinical malaria of a schedule with a fractional third dose at Month 2 versus a schedule with 3 full doses (primary and secondary case definitions) over 12 months post-Dose 3.
- To assess the incremental vaccine efficacy against clinical malaria, over 7 and
 12 months post-Dose 3, of a schedule with a fractional third dose at Month 7
 versus a schedule with a fractional third dose at Month 2.
- To assess the incremental vaccine efficacy against clinical malaria, over 7 and 12 months post-Dose 3, of a schedule with a fractional third dose at Month 7 versus a schedule with 3 full doses.
- To assess the incremental vaccine efficacy against clinical malaria, over 12 months post-Dose 4, post-Dose 5 and post-Dose 6 of a schedule with a fractional third dose at Month 2 and yearly fractional doses versus a schedule with full doses at Month 0, Month 1, Month 2 and yearly full doses.
- To assess the incremental vaccine efficacy against clinical malaria, over 12 months post-Dose 4, of a schedule with a fractional third dose at Month 7 versus a standard schedule with 4 full doses at 0,1,2,20 months.
- To assess the vaccine efficacy and impact of each RTS,S/AS01_E schedule over the entire study period by measuring the efficacy against clinical malaria at Months 14, 20, 26, 32, 38 and 50.
- To assess the prevalence of *P. falciparum* infections of each RTS,S/AS01_E schedule at cross-sectional visits (monthly from Month 0-20 and every three months thereafter till study end).

204889 (Malaria-094) Statistical Analysis Plan

 To assess the vaccine efficacy against incident *P. falciparum* infections defined by positive blood slide over the entire study period.

• Immunogenicity: Immune response to the CS and HBs antigens

- To describe the antibody response to the anti-circumsporozoite protein of P. falciparum (anti-CS) for each schedule.
- To describe the antibody response to the hepatitis B surface antigen (anti-HBs) for each schedule.

• Safety and reactogenicity

- To assess the safety of RTS,S/AS01_E for each schedule in terms of serious adverse events (SAEs), unsolicited adverse events (AEs) and AEs of specific interest.
- To assess the reactogenicity of RTS,S/AS01_E in terms of solicited local and general AEs.

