5.2. Secondary endpoints

• Efficacy:

- The occurrence of clinical malaria meeting the primary and secondary case definitions from Day 0 up to Month 50.
- The occurrence of incident *P. falciparum* infections from Day 0 to Month 50.
- The prevalence of *P. falciparum* infections defined by positive blood slide at each cross-sectional survey.
- **Immunogenicity**: Immune response to the CS and HBs antigens (immunogenicity subset)
 - Anti-HBs antibody concentrations, seropositivity and seroprotection measured before Dose 1, one month post-Dose 2 (group Fx017-20 only), before and one month post-Dose 3, before and one month after Dose 4, before and one month after each yearly dose and at study end (Month 50).
 - Anti-CS antibody concentrations and seropositivity measured before Dose 1, one month post-Dose 2 (group Fx017-20 only), before and one month post-Dose 3, before and one month after Dose 4, before and one month after each yearly dose and at study end (Month 50).

• Safety

- The occurrence of SAEs (all, fatal and related) during the whole study period according to the Medical Dictionary for Regulatory Activities (MedDRA) classification.

204889 (Malaria-094) Statistical Analysis Plan

- The occurrence of AEs and SAEs leading to withdrawal from further vaccination from Dose 1 (Day 0) up to Month 50, according to the MedDRA classification.
- The occurrence of severe malaria cases and cerebral malaria cases during the whole study period.
- The occurrence of potential immune-mediated diseases (pIMDs) from Day 0 up to Month 50, according to the MedDRA classification.
- The occurrence of meningitis from Day 0 up to Month 50, according to the MedDRA classification.
- The occurrence of seizures within 30 days (day of vaccination and 29 subsequent days) after each dose of study vaccine, according to the MedDRA classification.
- The occurrence of generalized convulsive seizure within seven days (day of vaccination and six subsequent days) after each dose of study vaccine, according to the Brighton collaboration guidelines [Bonhoeffer, 2004].
- The occurrence of unsolicited AEs within 30 days (day of vaccination and 29 subsequent days) after each dose of study vaccine, according to the MedDRA classification.

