		vac6→ser10 (m50) is outside [+308-420 days]	
		• Fx017- 20:	
		vac2→ser2(M2) is outside [21-35 days]	
		vac3→ser4 (M8) is outside [21-35 days]	
		vac4→ser6 (M21) is outside [21- 35 days]	
		vac5→ser7 (M33) is outside [21- 35 days]	
		vac5→ser9 (M50) is outside [+476-616 days]	
2100	Serological results	All visits where serum samples are	Immunology
	not available post-	planned (see Table 1– time points for	
	vaccination if ALL are missing and subject in Immunogenicity	immunogenicity)	
2120	Subset	All vigits where some someles are	Immunalagy
2120	Incomplete assessment and mislabelling (sample	All visits where serum samples are planned (see Table 1– time points for immunog enicity)	Immunology
	tested/not tested) of		

Code	Condition under which the code is used	Visit (timepoints) where the code is applicable	Applicable analysis set
	blood sample, for specific assays		

Code	Condition under which the code is used	Visit (timepoints) where the code is applicable	Applicable analysis set
3100	Subjects without follow up data starting 14 days post dose 3 Note that subjects not receiving dose 4, 5 and 6 will be censored at the last contact prior to whichever first missed dose recorded	 Applies under following conditions: First 3 vaccinations are administered No data available 14 days after visit 4 for Control, R012-20, R012-14, Fx012-14 No data available 14 days after visit 10 for Fx017-20 	Efficacy
3200	Subjects not receiving first 3 doses	 Applies under following conditions For control, R012-20, R012-14, Fx012-14 → no vaccination administered at visit 2,3 and 4. For Fx017-20 → no vaccination administered at visit 2,3 and 10 	Efficacy

^{*}a Dynamic elimination approach will be used for the definition of the immunogenicity PPS (Analysis M21 E1_02, Analysis M33 E1_03, Final analysis). This means that for codes 1040, 1070, 1080,1090, 2080, only the data relevant/posterior to the deviation will be eliminated. For codes 2040, 2090, 2120, the data elimination will be visit specific. For the efficacy PPS subjects will be fully excluded based on the elimination codes. However, subjects included in the efficacy analysis could be censored at last contact date.

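### SAP 7.4 gives no confidence interval for the change in antibody response from one dose to the next, although the protocol says the trial addresses hyporesponsiveness and the paired samples are taken

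*SAP*

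**What the plan says.** Protocol 1.2 lists three EMA requests. The second concerned "the efficacy and safety of multiple yearly doses and whether the vaccine predisposes to some degree of hyporesponsiveness to sequential doses". The section continues: "The current study is designed to address these points in the pediatric population". The immunogenicity objective is narrower and descriptive: "To describe the antibody response to the anti-circumsporozoite protein of P. falciparum (anti-CS) for each schedule" (SAP 3.2), with a parallel objective for anti-HBs. The objectives, the endpoints and the SAP do not mention hyporesponsiveness.

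The sampling is paired. SAP 5.2 times the measurements "before and one month post-Dose 3, before and one month after Dose 4, before and one month after each yearly dose and at study end". From the sampling table in SAP section 2, the pre/post pairs are:

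- R012-14 and Fx012-14: M2/M3, M14/M15, M26/M27, M38/M39 (Doses 3 to 6)
- Fx017-20: M7/M8, M20/M21, M32/M33 (Doses 3 to 5)
- R012-20: M2/M3, M20/M21 (Doses 3 and 4)

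Protocol 6.7.4.1 places all of these assays in the first 50 children enrolled per group.

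The analysis is by visit. SAP 7.4.2 says "GMCs and associated two-sided 95% CIs will be computed for each group at each available immunogenicity monitoring timepoint", each with a one-sample interval on the log10 scale. SAP 7.4.1 adds seropositivity and seroprotection rates, reverse cumulative curves and avidity summaries. The PPS is primary and the ES is also analysed. For the immunogenicity PPS, the footnote in SAP 6.2.2 says that for some elimination codes "only the data relevant/posterior to the deviation will be eliminated"; for others, removal is specific to the visit. SAP section 10 adds no paired or dose-to-dose analysis. The only GMC-ratio text in the annex is a decimals rule (11.1.3.4) and a conditional rule for between-group ratios (11.1.4.3).

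**The concern.** Whether the response weakens with successive doses is naturally a within-child comparison: the level after one dose set against the level after the previous dose in the same child. Two GMCs with separate intervals show the two levels but not the uncertainty of the change. That uncertainty depends on the within-child correlation, which no listed output reports. The two GMCs also need not cover the same children, because samples go missing and, in the PPS, data are eliminated as deviations accumulate.

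Without a pre-specified measure of change, the report would have to answer the regulator's question by eye from side-by-side GMCs, or by ratios chosen after the data are seen.

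**Working it through.** **Inputs.** Protocol 11.4 gives a post-vaccination anti-CS GMC of about 50, a log SD of 0.5, 50 subjects per group and a stated 95% CI of 36.3 to 68.8. The documents give no within-child correlation r, so I assume 0.3, 0.5 and 0.7. I also assume an SD of 0.5 at both visits and 50 complete pairs.

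**Step 1: reproduce the plan's figure.** 50 × 10^(±1.96 × 0.5/√50) = 36.3 to 68.8. This matches, and confirms base 10. Natural logs would give 43.5 to 57.4. The figure is the precision of one GMC at one visit; no precision is given for a change between doses.

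**Step 2: unpaired ratio of two GMCs.** The half-width on the log10 scale is t(98) × 0.5 × √(2/50) = 1.984 × 0.1 = 0.198. The interval around a ratio of 1 is 10^(±0.198) = 0.63 to 1.58. The ratio excludes 1 when the fall exceeds 1 − 0.633 = 37%.

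**Step 3: paired ratio.** The SD of the within-child log10 difference is 0.5 × √(2(1 − r)), and the half-width is t(49) × SD/√50, with t(49) = 2.01.

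| r | SD of difference | 95% CI around ratio 1 | Fall that excludes 1 | 95% CI at observed ratio 0.70 |
|---|---|---|---|---|
| unpaired | – | 0.63 to 1.58 | 37% | 0.44 to 1.11 |
| 0.3 | 0.592 | 0.68 to 1.47 | 32% | 0.48 to 1.03 |
| 0.5 | 0.500 | 0.72 to 1.39 | 28% | 0.51 to 0.97 |
| 0.7 | 0.387 | 0.78 to 1.29 | 22% | 0.54 to 0.90 |

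**Step 4: fewer pairs.** With 40 complete pairs the lower limits around a ratio of 1 are 0.65, 0.69 and 0.75, so the falls that exclude 1 become about 35%, 31% and 25%.

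**The case against.** Several points on the other side are sound.

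- **The point estimate is nearly available.** In children with both samples, the geometric mean of the within-child ratios equals the ratio of the two GMCs. A reader might infer that the dose-to-dose change cannot be obtained at all. That goes too far: what is missing is the interval and the restriction to common children.
- **The gain from pairing is moderate.** A reader might infer that only a near-halving would show, because two separate 95% CIs (each a factor of 1.387) stop overlapping at a 1.387² = 1.92-fold difference, a fall of 48%. The SAP states no non-overlap rule, and that rule is stricter than a comparison at the 5% level. The fair benchmark is 37%. At r = 0.3 pairing improves on it by only about 5 percentage points.
- **Successive GMCs are not from unrelated children.** Most dynamic elimination codes remove data from a deviation onward, so later sets are largely subsets of earlier ones. The ES analysis avoids these codes. Missing samples still affect both sets.
- **The regulator's request is not ignored.** Efficacy against Control after Doses 4, 5 and 6 (SAP 7.3.2.1 and 7.3.2.2) and six-monthly piecewise hazard ratios (SAP 7.3.2.6) bear on diminishing benefit. They do not measure the antibody response to each dose.
- **An unpublished table is possible.** The table list is held outside the SAP (SAP 11.2) and Protocol 11.9 ends in a redaction. SAP 7.4, which sets out the methods, shows no redaction and describes no such ratio.

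**Conclusion.** The gap is real but modest. The protocol claims the question, the design supplies the paired data, and the SAP as published specifies no interval for the dose-to-dose change and no common-subject comparison. Pairing lowers the fall that can be distinguished from no change from about 37% to between 22% and 32%. This rests on the protocol's SD applying at both visits, 50 complete pairs and an assumed correlation of 0.3 to 0.7.

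Neither document defines hyporesponsiveness as a within-child ratio, and the objective is only to describe, so this is a missing descriptive estimate and not a failed test. A reader might infer that a planned result is biased. None is: the planned GMCs are valid for what they summarise, and the primary and hierarchical efficacy tests do not depend on them. Label: cheap improvement.

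**What to change.** Add to SAP 7.4.2, as descriptive output for anti-CS and anti-HBs, within-child geometric mean ratios with paired 95% CIs in children with both samples, on the PPS and the ES:

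- post-Dose 4 / post-Dose 3: R012-20, R012-14, Fx012-14, Fx017-20
- post-Dose 5 / post-Dose 4: R012-14, Fx012-14, Fx017-20
- post-Dose 6 / post-Dose 5: R012-14, Fx012-14 (the other groups have no Dose 6)
- post-dose / pre-dose for each dose sampled, by group

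State that these ratios are the descriptive answer on hyporesponsiveness, and show the number of pairs behind each. The cost is a few SAP lines and one extra table per antigen, with no new samples, assays or visits. The limitation is that each ratio uses only children with both samples.

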7.5. Analysis of safety and reactogenicity

7.5.1. Analysis of safety and reactogenicity planned in the protocol

The primary analysis of safety will be based on the ES. Analyses containing only solicited data will be based on the solicited safety set.

Among the reactogenicity sub-cohort (first 50 subjects enrolled in each group) the percentage of subjects with at least one local AE (solicited and unsolicited), with at least one general AE (solicited and unsolicited) and with any AE during the solicited follow-up period (i.e. four days post-Dose 3, Dose 4, Dose 5 and Dose 6) will be tabulated with exact 95% CI after each vaccine dose and overall. The percentage of doses followed by at least one local AE (solicited and unsolicited), by at least one general AE (solicited and unsolicited) and by any AE will be tabulated for the whole solicited follow-up period (i.e. four days post-Dose 3, Dose 4, Dose 5 and Dose 6), with exact 95% CI. Similar tables will be generated for Grade 3 AEs and AEs considered as causally related to vaccination.

Among the reactogenicity sub-cohort (first 50 subjects enrolled in each group), the percentage of subjects reporting each individual solicited local and general AE during the solicited follow-up period (i.e. four days post-Dose 3, Dose 4, Dose 5 and Dose 6) will be tabulated with exact 95% CI. The percentage of doses followed by each individual solicited local and general AE will be tabulated for each dose and for the whole solicited follow-up period (i.e. four days post-Dose 3, Dose 4, Dose 5 and Dose 6), with exact 95% CI. Similar tables will be generated for Grade 3 AEs, causal events and for fever, temperature in 0.5°C increments.

The verbatim reports of unsolicited symptoms will be reviewed by a physician and the signs and symptoms will be coded according to the MedDRA. The percentage of subjects with at least one report of an unsolicited AE classified by the MedDRA preferred term level, occurring within 30 days (day of vaccination and 29 subsequent days) after each dose of study vaccine will be tabulated with exact 95% CI.

204889 (Malaria-094) Statistical Analysis Plan

The percentage of subjects reporting an SAE (all, fatal, related) occurring within 30 days (day of vaccination and 29 subsequent days) after each dose of study vaccine, classified by the MedDRA preferred term level will be tabulated with exact 95% CI.

The percentage of subjects reporting an SAE (all, fatal, related) from Dose 1 (Day 0) until Month 14, from Day 0 until Month 21, from Day 0 until Month 26, from Day 0 until Month 33 and over the whole study duration (Dose 1 [Day 0] until Month 50), classified by the MedDRA preferred term level, will be tabulated with exact 95% CI.

The percentage of subjects reporting an AE or SAE leading to withdrawal from further vaccination from Dose 1 (Day 0) until Month 50, classified by the MedDRA preferred term level, will be tabulated with exact 95% CI.

The percentage of subjects reporting severe malaria cases and cerebral malaria cases from Day 0 up to Month 14, Day 0 up to Month 21, Day 0 up to Month 26, Day 0 up to Month 33 and Day 0 up to Month 50 and over successive years within the study will be tabulated with exact 95% CI.

The percentage of subjects reporting pIMDs from Day 0 up to Month 14, Day 0 up to Month 21, Day 0 up to Month 26, Day 0 up to Month 33 and Day 0 up to Month 50, classified by the MedDRA preferred term level will be tabulated with exact 95% CI.

The percentage of subjects reporting meningitis from Day 0 up to Month 14, Day 0 up to Month 20, Day 0 up to Month 26, Day 0 up to Month 32 and Day 0 up to Month 50 classified by the MedDRA preferred term level will be tabulated with exact 95% CI.

The percentage of subjects reporting seizures occurring within 30 days (day of vaccination and 29 subsequent days) after each dose of study vaccine, classified by the MedDRA preferred term level will be tabulated with exact 95% CI.

For generalized convulsive seizures occurring within seven days following a dose of study vaccine, an analysis will be performed based on the Brighton Collaboration guidelines [Bonhoeffer, 2004]. This includes descriptive tables of the time relationship of seizures to vaccination, the duration of seizures and the level of diagnostic certainty.

Biochemistry (ALT, creatinine) and hematology (hemoglobin, WBC, platelets) values that are outside of the reference ranges (see protocol section 7.5.2.1) will be described for the reactogenicity sub-cohort (first 50 subjects enrolled in each group) before Dose 3, seven days post-Dose 3 and 30 days post-Dose 3. Frequency distribution of results by toxicity grades will be tabulated by group.

